Establishing Accuracy Parameters of a Child Social Communication Assessment Tool Research Protocol v2.0

[name],

Consultant Community Paediatrician, Sussex Community NHS Foundation Trust and Honorary Lecturer **Brighton and Sussex Medical School.**

[name].

Senior Research Fellow, Sussex Community NHS Foundation Trust and Brighton and Sussex Medical School.

Funded by the BMA Helen A Lawson Award

Summary of research project

Autistic Spectrum Disorders (ASD) affect at least 1.1 % of the population (CDC, 2014). NICE recommends that diagnosis requires a multidisciplinary team assessment, obtaining information from various settings including home and school, as well as testing for evidence of autistic behaviours and patterns of thinking (NICE, 2011). Various tools have been developed to aid this process including observational tools such as the Autism Diagnostic Observation Schedule (ADOS). This is a lengthy process, our own study of practice in UK suggesting this takes around 13 hours of professional time to complete, costing around £800 per child (Galliver et al., in submission). Most teams (10/12) employed a two-stage process including an initial screening clinic determining the need for the full multidisciplinary diagnostic assessment.

With diagnostic services reporting growing pressure to meet the growing level of demand, and families having to wait a long time (6 months to 2 years (Autism Achieve Alliance, 2014) for this to be completed, approaches that can improve decision making at initial contact could improve the patient journey and potentially reduce costs. We have developed an automated story that scores emotional cognition in children that could be used alongside parental history and school questionnaire at initial clinical contact, to support decision making. Initial pilot data in children attending for initial assessment for possible ASD, and in a sample of 32 children attending a local primary school, suggests good sensitivity (85%), specificity (92%), and parental and child acceptability in clinic and "typically developing" populations.

This study aims to expand the initial pilot study with increased sample size, testing its use in 62 primary school aged children with a diagnosis of ASD, and in a larger sample of typically developing children (n=62, total sample n=124) attending local primary schools.

Introduction (including the scientific background to the research question)

Background: Why is this Tool Needed?

Autistic Spectrum Disorders (ASD) affect at least 1.1 % of the population (Baird, 2006; Christensen et al, 2016) and could be even twice this figure allowing for possible under-representation, and improving recognition in girls. Affected children, and adults, would be expected to have difficulties in social interaction and communication particularly with their peer group, and repetitive and sensory behaviours, often described as "social communication difficulties". These difficulties can vary from a child with no speech who has minimal interaction with his peers, to a child who may be desperate to make friends but lacks the understanding as to how to do so, whilst having the language to describe their interests in extensive detail. In the absence of a diagnostic test, a multidisciplinary assessment process is recommended in the UK. This requires information being gathered from various environments including home and educational settings, as well as observation and testing for evidence of autistic behaviours and/or patterns of thinking in clinic (NICE, 2011). Various tools have been developed to aid this process including formal structured history tools such as the Autism Diagnostic Interview (ADI-R) and the Diagnostic Interview for Social Communication Disorders (DISCO), and observational tools such as the Autism Diagnostic Observation Schedule (ADOS) and the NEuroPSYchological developmental assessment (NEPSY). However, as NICE recognised, "no single tool alone seems to have adequate sensitivity and specificity for diagnosis of autism" (NICE, 2013).

The multidisciplinary process is lengthy. Our own study of practice in UK based Child Development Centres suggests this takes around 13 hours of professional time to complete costing around £800 per child (Galliver et al., in submission). We also identified that most teams (10/12) employ a 2-stage process (see figure 1) including an initial, "Stage One", screening or general developmental clinic which typically lasts 60-90 minutes (cost £100). This is often carried out by a paediatrician working alone where a decision is made about whether to proceed to the full multidisciplinary diagnostic assessment (NICE, 2011). At the initial clinic, the clinician may have access to information from validated screening questionnaires such as the Social Communication Questionnaire (SCQ) (Chandler et al, 2007) giving a parental perspective of the child, and information from an educational setting (often also in questionnaire form). However, the clinician largely relies on taking a broad developmental history from the parent/carer and observation of the child in clinic. A full "Stage Two" diagnostic assessment may include a paediatrician, a speech therapist and clinical psychologist and others (NICE, 2011), using formal history taking which specifically addresses the presence of autistic symptoms and formal observational assessment for signs of autism, and may include observation and discussion in the child's educational setting.

The combination of lengthy process and steady increase in referrals has placed diagnostic services under increasing pressure resulting in waiting times for complete assessment in the UK taking between 6 months and 2 years (Autism Achieve Alliance, 2014). Therefore, approaches that ease pressure on diagnostic pathways, e.g. by improving decision making at Stage One assessment, may potentially improve the quality and speed of the patient journey through the system and reduce costs. The importance of this for parents is reflected in an on-line survey we have just completed, (N =90) giving a mean rating score of

[figure not shown]
5.8/7 (scale 1-7) on the need to for research questions that could improve diagnostic pathways. Individual responses included:

"How can we identify autism more efficiently?"

"Early intervention is known to be important, yet diagnosis seems to be delayed again and again with a 'wait and see' approach. Why is this?"

"Why do families have to wait so long for a diagnosis?"

11-12hrs/child (cost £700/child)

Multi disciplinary Paediatrician + SALT/Clin Psych +/- OT, support worker, psychiatrist etc

Autism specific structured history from parents eg 3DI, ADI

Autism Specific Observation of child eg ADOS, NEPSY School/Preschool Observation, picture from teachers

Figure 1. Example diagnostic pathway

The Automated Story: A Pirates Adventure

We conducted a detailed review of literature underpinning psychometric assessment of children with possible ASD. From this, storyboards were constructed incorporating identified tests, adapted into the context of a pirate adventure story line (Jordan et al, 2016). This includes tests of:

- Affect recognition (Golan et al, 2010), including ability to match facial expressions (see figure one), short-term recall of facial expression, and to identify appropriate situational facial expression.
- First Order Theory of Mind, adapting the "unexpected contents (Smarties tube) task" (see figure two) and Sally Ann tests (Baron-Cohen et al, 1985)
- Second Order Theory of Mind (Wimmer and Perner, 1985)
- Strange Stories exploring the child's ability to recognise and explain the use of sarcasm and a lie (Happé, 1994)
- Understanding of Idiom, such as "the treasure cost him an arm and a leg" (Barton, 2012)

We further explored principles of software design for children on the autistic spectrum. Design features likely to improve engagement, and which we've adopted for the software design, included:

- Text should be concise, literal and unambiguous, readable and avoiding capitalising whole sentences
- Navigation should be clear, e.g. using tap or swipe with clear prompts e.g. buttons or arrows. Buttons should be large and finger friendly
- Design features should include: uncluttered layout, engaging format and story line, clear feedback (e.g. progress bar), visual images, simple colour palette avoiding black text on white background (visually over stimulating), using easily readable font such as Sans Serif, no time restrictions and no penalising ("errorless learning"), avoiding flashing, fast animations (avoiding sensory overload), and abrupt changes, whilst using prompting and reinforcement (Fletcher-Watson, 2015).

The resulting scenarios were built into a sequential pirate adventure story line, incorporating the recommended design features, e.g. a Flesh-Reading Ease score of 93.7 (0 unreadable, 100 most readable).

Early use in 3 local Child Development Clinics suggested that the tool can help inform decision making around the need for further diagnostic assessment when used alongside parental history and information from other settings such as school questionnaires. In addition to information obtained from the questions within the tool, clinicians commented that they often obtained additional information around the child's interaction with themselves and with the tool. This experience, together with consultation with our wider team, including an academic expert in psychological testing, including Theory of Mind, ([name]), [name] (Head of OT, Royal Free), [name] (expert in use of digital technology in autism), and local parents, has allowed us to modify the story lines.

[figure not shown]

Figure 2. Affect recognition page

[figure not shown]
Figure 3. First Order Theory of Mind Test page adapted from Unexpected Contents False Belief Task.

Initial Pilot Study

(IRAS 217324 REC 16/LO/2138; HRA 201701014).

Pilot data, testing Pirates in 32 typically developing children (TD) attending a mainstream primary school (ages 4-11 years), and children attending the Child Development Centre following referral for possible ASD/social communication difficulties (ASD) showed a strong negative correlation (p<0.001) between number of errors and age (see figure 4), with most key stage one children (4-7.4 years) making 7 or fewer errors, and key stage two (7.5-11 years) less than 4. Taking data from children attending clinic for possible ASD in current study, suggests that most children where there were concerns about social communication were scoring at a higher level than this. Using the cut off scores identified in this study gave sensitivity 85%, specificity 92%, NPV 94%, PPV 79% which if confirmed in the proposed study would give a favourable performance in comparison with current screening tools such as the SCQ. By relating individual scores to these cut offs showed that typically developing children made a mean 1.9 (CI -2.5 to -1.3) fewer errors than the cut off, whilst children considered likely to have ASD clinically made a mean of 3.9 (CI 1.4 to 6.2) errors above the cut off, the difference being highly statistically significant (t test, p<0.00001). Children reported enjoying completing Pirates, whilst parents reported this increased their confidence in clinic assessment.

[figure not shown]

Figure 4. Total score compared to age in months

Accuracy Parameters Protocol Version 2 29/9/17

a) Pilot study data only. b) includes data from early clinical use prior to pilot study

Aims and objectives

Test automated story with children in mainstream school, and with those already diagnosed with autistic spectrum disorder (ASD) in child development centres (CDCs).

- 1. Primary objective: Investigate parameters of screening tool in a group of 4 to 11 year old children, i.e. of primary school age, with known ASD; estimate discrimination from a group of children who are "typically developing", i.e. who do not have a clinical diagnosis of ASD.
- 2. Assess sensitivity/specificity of individual questions and relationship to age e.g. even typically developing younger children may not understand idiom.

Project design

Research methods

1. Sensitivity and Specificity of screening tool

User testing, two groups (children with a diagnosis of Autism Spectrum Disorder (ASD), typically developing children with no diagnosis (TD)) recruited to assess sensitivity of the automated story in a) a clinical environment (ASD, N=62), b) and in a school setting (TD, N=62).

Ethical approval

This has already been achieved for the initial pilot study in an investigation of typically developing children and children referred to a child development clinic for social communication difficulties (IRAS 217324 REC 16/LO/2138; HRA 201701014). We now hope to extend this to the proposed study through substantial amendment. The main change from the original pilot study is to change the "clinical group" from children referred for initial assessment of possible ASD to children already diagnosed with autism spectrum disorder. The methodology is essentially unchanged.

Subjects (including justification for sample size)

A sample of 124 children, suggested after consultation with Research Design service and Medical Statistician, with 62 typically developing children (31 male, 31 female), 62 with ASD (31 male, 31 female) aged 4 to 11 years will be recruited. With 62 children in each group, we will be able to further estimate the sensitivity and specificity of the software result with sufficient precision to enable us to isolate key parameters (Teare et al, 2014). For example, following Buderer (1996) with 62 ASD and 62 typical (i.e. a prevalence of ASD of 50%), assuming a sensitivity of 80%, the 95% confidence interval (CI) for sensitivity

would be from 70 to 90%. The same applies for specificity. For this first stage, we aim to cluster children into two groups from the results of the application: "at risk/no risk" of ASD, which should match with ASD/No ASD. These two groups would then be further analysed against results to see if there is specific clustering around certain scores (total score, and for individual questions/sections), or responses, that may relate to other common associated impairments and co-morbid conditions which are: learning difficulty, language impairment, attention deficit hyperactivity disorder.

Recruitment

Children aged 4 to 11 years with ASD will be identified through CDCs in Sussex Community NHS Trust, by paediatric clinicians; typically developing children will be identified through the headteacher/appropriate member of staff in mainstream primary schools. The parents of children identified will be given a participant information sheet, and asked to contact the research team if they are interested in taking part. We estimate that we will need to approach 240 parents to achieve the full sample of 120 children. This is based on previous local recruitment rates for neuro-disability research of approximately 50% response. We will need to approach 12 potential recruits per month, with 6 recruited per month or 1.5 per week. This means the recruitment and data collection will be spread over 24 months, which we believe is feasible. We will aim to recruit and case match by age and gender.

Information leaflets will be given to the clinical group either in clinic by a member of the clinical care team or from the clinical team by post. Following this, parents will be contacted by the research team, and written informed consent will be sought. The pirate app testing will take place either in the home, clinic or school depending on adult preference.

Children in school will be given study information via school. Parents will then be contacted by the research team to discuss the study and if appropriate consent will be returned to school and then handed to research team. Phone contacts may be made to remaining parents to seek consent, where appropriate.

Inclusion criteria

Children aged 4 to 11 years, of primary school age:

- Group One: ASD: children with a recently confirmed diagnosis of ASD. Diagnosis will have involved full multidisciplinary diagnostic assessment by a CDC.
- Group Two: Typically developing group attending mainstream school

Exclusion criteria

- Child non-verbal or severe learning difficulties or English as second language;
- Typically developing children with prior referral to a child development team or with known social communication or language difficulties or ADHD. These children may take part but results will not be included in typically developing results for analysis.
- Child not of primary school age (i.e. 4 to 11 years).

Process of gaining consent

All necessary consents will be obtained from parents and children following research ethical approval in advance of recruitment and data collection. Individual school policy will be followed for consenting and acceptability of school recruitment. A member of the team experienced in education will lead school recruitment (ex-Assistant Head teacher). Parental consent and child assent will be sought. Two schools in the local area have indicated interest in the study giving a potential recruitment base of 800 children.

Test

Participants in both groups will be given the screening tool to complete. A medical researcher will administer the application to children with ASD and typically developing children in clinic and/or in schools or in the child's home. The story produces pass/fail results recorded anonymously within the software. This data will be transferred to a paper record, and automatically deletes from the software once the individual testing is completed. Current cut-offs are set at 7 errors for key stage one children (4-7.4 YO) and 4 errors for key stage two (7.5-11YO). Results will be collated to attempt to see if it is possible for scores to cluster clearly around typical and ASD populations. There is already evidence of clustering for a clinically abnormal versus typically developing population.

Data analysis

Quantitative Analysis

The main aspects of data recorded will analyse the ASD group: SCQ score, clinical notes confirmation of ASD (yes/no), and automated story result (at risk of ASD yes/no using cut-off scores). Typically developing group will be scored only on automated story result (given that there has been no clinical contact). These will be used to assess sensitivity and specificity with three levels of cross sectional analysis:

- a) Clinical notes diagnosis (i.e. does school observation support diagnosis Yes/No) vs. automated story result
- b) SCQ score vs. automated story result
- c) SCQ score + clinical notes (i.e. does school observation support diagnosis Yes/No) vs. automated story result

We will also calculate positive and negative predictive values. Sensitivity of the instrument with correct case finding will be based on clustering on types of ASD and typically developing children.

For this stage we aim to cluster children into two groups from the results: "at risk/not at risk" of ASD, which should match with ASD/Typically Developing.

These two groups would then go into secondary analysis to consider if there is clustering around certain scores or answers, and future study will explore relationship to other common associated impairments and co-morbid conditions such as: learning difficulty, language impairment, attention deficit hyperactivity disorder. We will estimate proportions of pass/fail recruited and retained for the clinical study and estimate sensitivity and specificity i.e. where sensitivity is the proportion of children with ASD that the tool correctly identifies, and specificity is the proportion without ASD that the screening tool correctly identifies. Thresholds and potential cut-off points for scores will be further clarified and defined using Receiver Operating Characteristic curves will to help refine the tool by comparing sensitivity/specificity and enable appropriate cut-offs to be decided. A logistic regression model will also be fitted to understand accuracy where the result of the tool is the predictor variable and we will also adjust for age and gender, as the at-risk of ASD and typically developing will be matched on these. If the tool detects accurately we will then aim to acquire European medical device regulation 93/42/EEC(MDD)8 for clinical trials [46]. If sensitivity/specificity trial is successful, the equipment will be used in a planned clinical trial.

Potential of research for patient care

Improving information at initial screening will reduce stress and anxiety for children and families and improve the experience and engagement of children. Further, quicker and better decision making will aid in determining which children require full assessment.

References

Autism Achieve Alliance (2014) Autism Spectrum Disorders: Waiting for assessment. Executive Summary, 6 August 2014 (accessed 26/2/2016)

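### The study contrasts confirmed ASD with school children screened free of related difficulties, so it cannot confirm the pilot's accuracy or show performance at Stage One, where the tool is meant to be used

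*Protocol*

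**What the plan says.** **Intended use.** The background section hopes to ease pressure on diagnostic pathways "by improving decision making at Stage One assessment". The section on potential for patient care says that "quicker and better decision making will aid in determining which children require full assessment". Both concern children already referred.

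**Who is analysed.** Under Inclusion criteria, Group One is "children with a recently confirmed diagnosis of ASD", made by full multidisciplinary assessment, and Group Two is "Typically developing group attending mainstream school". Exclusion criteria then deals with school children who have had a prior referral to a child development team, or who have known social communication or language difficulties or ADHD: "These children may take part but results will not be included in typically developing results for analysis". No use of their results is stated there.

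**How the change is described.** Under Ethical approval, the main change from the pilot is from "children referred for initial assessment of possible ASD to children already diagnosed with autism spectrum disorder". The next sentence reads "The methodology is essentially unchanged".

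**What is expected.** Initial Pilot Study reports sensitivity 85%, specificity 92%, NPV 94% and PPV 79%, "which if confirmed in the proposed study would give a favourable performance in comparison with current screening tools such as the SCQ". Data analysis plans predictive values and makes a device-regulation step and a planned clinical trial depend on a good result.

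**The concern.** At Stage One the difficult task is to separate referred children who have ASD from referred children who do not. Many of the latter may have language difficulties, ADHD or other social communication problems. The analysed control group is defined by the absence of those features. A tool that scores emotion recognition, theory of mind and idiom will probably flag fewer of these controls than it would flag among referred children without ASD.

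The result is also the gate to the next step. If a specificity obtained this way is presented as confirming the pilot, or as better than the SCQ, that step rests on a figure that does not apply to the intended setting. The protocol nowhere warns that the estimates may not carry over to referred children.

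**Working it through.** **1. The plan's own precision figure.** Inputs from Subjects: 62 per group, assumed sensitivity 80%, 95% CI.

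Half-width = 1.96 × √(0.80 × 0.20 / 62) = 0.0996, so the CI is 70.0% to 90.0%. This matches the stated 70% to 90%. The arithmetic is sound, but it covers sampling error only and says nothing about which children are sampled.

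**2. The two contrasts side by side.**

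| | Stage One use | This study |
|---|---|---|
| With ASD | referred, not yet diagnosed | diagnosis already confirmed |
| Without ASD | referred, found not to have ASD | school children; prior referral, social communication or language difficulties and ADHD left out |

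The study has no counterpart to the lower middle cell.

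**3. Does the pilot's 92% come from the same kind of controls?** The pilot had 32 typically developing school children, and its 2×2 table is not given. With 32 as denominator, 29/32 = 91% and 30/32 = 94%; no count gives 92%. I searched for whole-number tables that round to all four pilot figures. The smallest are:

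- 11/13 with ASD flagged and 33/36 without ASD not flagged: 85%, 92%, PPV 11/14 = 79%, NPV 33/35 = 94%.
- 11/13 and 34/37: 85%, 92%, PPV 11/14 = 79%, NPV 34/36 = 94%.

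The next have 97 to 101 children in total. So the pilot's non-ASD group was probably larger than the 32 school children. It may have included clinic children or early clinical data, but the documents do not say.

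**4. Predictive values move with the group mix alone.** With sensitivity 0.85 and specificity 0.92, solving the two formulas for the ASD share p:

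- PPV = 0.85p / (0.85p + 0.08(1 − p)) = 0.79 gives p = 26%.
- NPV = 0.92(1 − p) / (0.92(1 − p) + 0.15p) = 0.94 gives p = 28%.

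This study fixes p at 50%. With the same 85% and 92%, PPV = 0.85 / (0.85 + 0.08) = 91% and NPV = 0.92 / (0.92 + 0.15) = 86%. PPV rises from 79% to 91% with no change in the tool.

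**5. Illustration of what a lower Stage One specificity would mean.** PPV = Se·p / (Se·p + (1 − Sp)(1 − p)). Sensitivity 80% is the protocol's planning value and 92% is the pilot specificity. The ASD shares and the lower specificities are assumptions.

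| Specificity | ASD share 30% | 50% | 70% |
|---|---|---|---|
| 92% | 81% | 91% | 96% |
| 80% | 63% | 80% | 90% |
| 70% | 53% | 73% | 86% |

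At 50%, for example: 0.40 / (0.40 + 0.04) = 91%, against 0.40 / (0.40 + 0.15) = 73%.

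**The case against.** The strongest reply is that the protocol is open about its staging. The primary objective is discrimination of known ASD from typically developing children, the sample-size text calls this a first stage, and a clinical trial is to follow. That stands. The design is legitimate for its stated objective and need not change.

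A reader might infer that calling the methodology essentially unchanged is simply false. The text does not support that. The preceding sentence names the new clinical group as the main change and submits it as a substantial amendment, so the phrase can fairly be read as meaning the test procedures. It needs limiting to them, because in an accuracy study the choice of children is part of the method.

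A reader might also infer that the pilot made a much harder comparison. That is not shown: the pilot too used school children. If all 32 are in the smallest tables above, only 4 or 5 other non-ASD children contributed, and larger tables fit as well.

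Nor can all the accuracy figures be called too favourable. Missing borderline cases could raise sensitivity, but the exclusion of non-verbal children and those with severe learning difficulties removes some of the most affected.

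The tool is meant to be used alongside history and school information, so its PPV alone does not settle its usefulness. Finally, the school children left out have no reference standard and no planned number, so they cannot supply Stage One specificity.

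None of this answers the Initial Pilot Study statement, which carries no limit on population.

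**Conclusion.** The point holds in a limited form. The analysed contrast differs from the intended use, specificity among referred children without ASD is not estimated, and the specificity obtained is likely to be higher than it would be there. This direction rests on the expectation that children with overlapping difficulties make more errors on the tool. The effect on sensitivity is uncertain.

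The documents give neither the ASD share among referrals nor specificity in referred children without ASD, so no corrected figure can be derived. The PPVs of 91% against 73%, at an assumed 50% share and an assumed fall in specificity from 92% to 70%, only show what could be at stake.

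The claim that this study could confirm the pilot's 85% and 92%, and thereby a favourable comparison with the SCQ, is not supported by the design. That the pilot's 92% came from a somewhat different non-ASD group is a probable inference from the rounding, not a stated fact.

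**What to change.** Keep the design and make two changes.

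1. **Wording**, in Initial Pilot Study, Ethical approval, Data analysis and the section on potential for patient care. State that the results estimate discrimination between known ASD and typically developing school children, are not Stage One accuracy, and will not be presented as confirming the pilot figures or as better than the SCQ in referred children. Limit the claim of unchanged methodology to the test procedures. Say that the planned later study must estimate accuracy in referred children.

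2. **One descriptive row.** At the current cut-offs, report the proportion flagged among school children who were tested but left out of the typically developing results and who have no reported ASD diagnosis. The Pirate Study Child Details form asks parents about ASD, social communication and language difficulties and ADHD. Label the row as a group without a reference standard, probably small, and do not call it specificity.

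The cost is a less favourable claim and one extra table row. No additional recruitment or testing is needed.

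### The Recruitment section plans for 120 children where the design requires 124, and its monthly rates do not match its 24-month duration; a minor correction of figures

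*Protocol*

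**What the plan says.** The sample size is given as 124 in two places. The Summary describes testing "in a larger sample of typically developing children (n=62, total sample n=124) attending local primary schools". The Subjects section repeats "A sample of 124 children" and divides it into two groups of 62, each with 31 boys and 31 girls. For 62 per group and an assumed sensitivity of 80%, it gives a 95% confidence interval of 70 to 90%, and says the same holds for specificity.

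The Recruitment section uses a different total: "We estimate that we will need to approach 240 parents to achieve the full sample of 120 children". It explains the yield: "This is based on previous local recruitment rates for neuro-disability research of approximately 50% response". It then sets the pace: "We will need to approach 12 potential recruits per month, with 6 recruited per month or 1.5 per week", and concludes that recruitment and data collection will run over 24 months.

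The Exclusion criteria add a provision for school children with a prior referral, known social communication or language difficulties, or ADHD: "These children may take part but results will not be included in typically developing results for analysis". No recruitment figure mentions them.

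**The concern.** Four cells of 31 make 124, so a sample of 120 cannot fill the design described in the Subjects section. The Recruitment section nevertheless treats 120 as complete and sizes the list of approaches to it. Its monthly rates, carried over the stated duration, imply a third total. A team working from this section would have no single figure to recruit to.

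The control group has a related ambiguity. Some school children may be tested but left out of the typically developing results, and the protocol does not say whether the 62 controls are counted before or after they are set aside. Specificity depends only on the analysable controls, so the 62 should refer to them.

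**Working it through.** **Inputs.** Target 124 = 62 + 62 (Summary; Subjects). Approaches 240, stated total 120, response about 50%, 12 approached and 6 recruited per month, 1.5 per week, 24 months (Recruitment). Assumed sensitivity 80%, stated interval 70 to 90% (Subjects). The share of school recruits set aside is not given.

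**1. Yield.** Yield = approaches × response.
- 240 × 0.50 = 120. The section's own figure reproduces.
- 120 is 4 short of 124.
- Approaches needed for 124: 124 / 0.50 = 248, which is 8 more than stated.

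**2. Rate and duration.** Total = monthly rate × months.
- Approached: 12 × 24 = 288. Recruited: 6 × 24 = 144. These match neither 240 and 120 nor 248 and 124.
- 144 − 124 = 20, so this mismatch is a surplus.
- Months needed at 6 per month: 120 / 6 = 20.0; 124 / 6 = 20.7.
- Rate needed over 24 months for 124: 124 / 24 = 5.2 recruited and 248 / 24 = 10.3 approached per month.
- 1.5 per week equals 6 per month only for a four-week month. On calendar months it is 1.5 × 52 / 12 = 6.5.

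**3. Precision.** Half-width = 1.96 × √(p(1 − p)/n), with p = 0.80.
- n = 62: 1.96 × √(0.16/62) = 0.0996, interval 70.0% to 90.0%. The stated interval reproduces.
- n = 60: 1.96 × √(0.16/60) = 0.1012, interval 69.9% to 90.1%. This still rounds to 70-90%.

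**4. Set-aside school children (assumed shares).** School recruits needed for 62 analysable controls = 62 / (1 − d), rounded up. The total adds 62 children with ASD, and approaches are twice the total.

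| Assumed share d | School recruits | Total recruited | Approaches | Months at 6 per month |
|---|---|---|---|---|
| 5% | 66 | 128 | 256 | 21.3 |
| 10% | 69 | 131 | 262 | 21.8 |
| 15% | 73 | 135 | 270 | 22.5 |
| 20% | 78 | 140 | 280 | 23.3 |

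The 144 implied by 6 per month over 24 months would cover a moderate share. Split evenly, it gives 72 controls and tolerates 1 − 62/72 = 13.9% set aside. With all 20 extra children in the control group it gives 82 and tolerates 1 − 62/82 = 24.4%.

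**The case against.** A reader might infer that the recruitment plan cannot deliver the sample and that precision will suffer. The documents do not support that, for five reasons.

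- **The rates over-deliver.** Six per month for 24 months gives 144, more than 124. Only the statement of 240 approaches for 120 children falls short. This objection stands.
- **Nothing stops recruitment at 120.** The figure appears once, in a sentence framed as an estimate and based on an approximate response. Reaching 124 from 240 approaches needs 124/240 = 51.7%, which is compatible with about 50%. This stands as to consequence, but the section still calls 120 the full sample.
- **Precision hardly changes.** Sixty per group still gives an interval that rounds to 70-90%. This stands.
- **A control shortfall is not shown.** The Operating Guidelines have staff check after consent, but before an ID is generated and before testing, whether a child can be in the control group. Set-aside children may therefore be additional to the 62. School staff identify typically developing children, and the consent section cites a potential base of 800 children, so the supply of controls is unlikely to be limiting. No set-aside share is stated, so any shortfall rests on an assumption. What remains is a need to say how the 62 are counted.
- **The 24 months also covers data collection.** About 21 months of recruitment plus slack is a possible reading. It is not what is written, since the section presents the 24 months as following from the monthly rates.

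**Conclusion.** The Recruitment section is wrong as written, with minor severity. Its total of 120 contradicts the 124 fixed elsewhere by 4 children, and its 240 approaches should be about 248 at the stated response. Its monthly rates over 24 months imply 288 approached and 144 recruited, which agree with no stated total. These conclusions need only the protocol's own figures.

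The statistical consequence is small: at 80% sensitivity, the half-width moves from 9.96 to 10.12 points if each group has 60 rather than 62. That comparison assumes the 120 would split equally, which the section does not say. The provision for set-aside school children calls only for a clarification that 62 means analysable controls. The allowances of 5% to 20% shown above are assumptions.

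**What to change.** Revise the Recruitment paragraph as follows:

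- Change 120 to 124 and 240 to about 248.
- Give one consistent pace: either 6 recruited per month for about 21 months, or about 5.2 recruited and 10.3 approached per month over 24 months. If the 24 months is meant to include time for data collection beyond recruitment, say so.
- State that the 62 controls are counted after the children described in the Exclusion criteria have been set aside. If extra approaches are planned for this, give the number and label the share as an assumption; for example, about 262 approaches in total if 10% of school recruits are set aside.

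The cost is corrected figures in one paragraph and a few more invitations: 8 more than now stated, or 22 more with the 10% allowance. The design and the precision statement do not change.
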